14.6.9 SCID

A SCID to assess the subject's cocaine-dependence according to DSM-IV criteria, severity of depression, and axis I disorders will be conducted during screening. The SCID will be

administered by a staff member with clinical experience in assessing subjects with psychiatric disorders.

14.6.10 ASI

The ASI Fifth Edition, 1997 version, will be administered by a research staff member having at least a bachelor's degree in the social sciences or equivalent training and experience as determined by the site's investigator. The ASI is used to evaluate treatment outcomes in seven areas (medical, employment, drug use, alcohol use, legal, family/social, and psychological). Composite scores will be calculated according to the procedures described by McGahan *et al.*,¹⁴ Carroll *et al.*¹⁵ A copy of the ASI manual and question-by-question guide may be found in the study operations manual.

14.6.11 Urine BE and Creatinine

Urine samples will be collected ideally at 48-hour intervals 3 times a week (generally Monday, Wednesday, and Friday, barring holidays and schedule conflicts). Two different types of collectors will be used, one at screening, Ontrak Testcups®, and one during treatment, Franklin Collectors. Ontrak Testcups ®provide for the rapid, simultaneous testing of multiple drugs with no urine or reagent handling, and obviate the need for direct observation of the individual. After testing, screening samples will be split at the sites: one-half of each sample will be stored frozen at the site for backup; the other half will be sent to a central laboratory for analysis. If the samples will not be shipped within 10 days of collection, they should be frozen until shipment. Otherwise the samples should be refrigerated until shipping.

The Franklin Collector, a device that documents specimen authenticity through the precise measurement of urine temperature will be used for all urine collections after screening and baseline. Direct observation, however, may be employed in lieu of the Franklin Collectors when urine temperature assessments may not be reliable or appropriate (e.g. pyretic individuals) or the collectors are unavailable.

If a subject fails to give a sample on the day it is due, it will be obtained as close to the missed visit as possible. Urine samples will be sent to a central laboratory to be analyzed for BE and creatinine. Approximately one-half of each urine sample will be frozen at the sites until the samples have been received and analyzed and the results recorded at the central laboratory. Results will not be provided to the individual sites during the study, and sites are prohibited from analyzing samples locally.

14.6.12 Urine Drug Screen (Qualitative Analysis of Substances of Abuse)

The first sample of each week taken for BE and creatinine analysis will be analyzed additionally for amphetamines, barbiturates, benzodiazepines, and opiates and each time during screening.

14.6.13 Self Report of Use (SUR)

The SUR includes the subject's daily report of use of cocaine, alcohol, marijuana, opioids, and nicotine since the last clinic visit.

14.6.14 BSCS

The BSCS is a self-administered assessment that asks the participant to rate his or her craving for cocaine. The BSCS used for this study is a modification of the State of Feelings and Cravings Questionnaire.¹⁶ If the participant is unable to self-administer this assessment (e.g., physical handicap, poor reading skills), study personnel can assist by reading the questions out loud to the participant and/or marking the participant's response on the CRF. However, study personnel are not to offer interpretations of the questions.

14.6.15 Clinical Global Impression-Observer (CGI-O)

The CGI-O requires the observer to rate the global severity of the subject's cocaine dependence symptoms and to rate the improvement of the subject's cocaine dependence since the beginning of the study. The severity of the subject's cocaine dependence is rated according to eight specific problem areas often associated with cocaine dependence. The CGI-O will be administered by an experienced staff member with clinical experience in assessing subjects with cocaine dependence.

14.6.16 Clinical Global Impression-Self (CGI-S)

The CGI-Self is a self-administered assessment that asks the participant to rate the global severity of his or her cocaine dependence symptoms and to rate the improvement of his or her cocaine dependence symptoms since the beginning of the study.

14.6.17 Adverse Events (AEs)

AEs will be assessed at each study visit by an investigative staff nurse or physician. If an AE is reported to a nurse that requires medical attention, it should be reported to a study physician immediately. A study physician will meet with the participant once a week to review the AEs recorded by the nurse and to assess for any additional AEs. The investigator or study physician will assess subjects for any medical or psychiatric side effects. Both the research assistant and physician will assess AEs by asking the participant "How have you been feeling since I saw you last". The type of AE, severity of the AE, and the relationship to the study treatments will be recorded on an AE CRF according to the procedures described in section 15.6.

14.6.18 Risk Assessment Battery (RAB)

The RAB is a self-administered assessment of the participant's engagement in activities that increase the likelihood of contracting HIV. If the participant is unable to self-administer this assessment (e.g. physical handicap, poor reading skills), study personnel can assist by reading the questions out loud to the participant and/or marking the participant's response on the CRF. However, study personnel are not to offer interpretations of the questions.

14.6.19 ECG

Twelve-lead electrocardiograms will be performed according to standard procedures. The results will be reviewed by the site physician for interpretation. The site physician may consult with a cardiologist on the results of the ECG if he/she feels that a consultation is necessary. ECG results will be used to assess cardiovascular anomalies during screening to assure that subjects do not meet exclusion criteria and at study completion to assess AEs.

14.6.20 Treatment Compliance-Drugs

Compliance with study agents will be determined by recording patch use at each visit.

14.6.21 Treatment Compliance-Therapy

Compliance with scheduled psychosocial therapy sessions will be monitored by recording the subject's attendance at sessions and the length of each session on the appropriate CRF.

14.6.22 Blood Selegiline/Selegiline Metabolite Levels

Analysis of selegiline, N-desmethylselegiline, L-amphetamine, and L-methamphetamine plasma concentration will be determined during screening and after 2 and 5 weeks of treatment. Blood should be collected prior to the first dose and within 15 minutes prior to the application of new patches during weeks 3 and 6. The analysis will be performed by the University of Utah, Center for Human Toxicology using a validated liquid chromatography atmospheric pressure chemical ionization tandem mass spectrometry measurement. The procedure for blood collection, storage, and shipping is provided in Appendix IV.

15 REGULATORY AND REPORTING REQUIREMENTS

15.1 FDA FORM 1572

The investigator at each study site will sign a Statement of Investigator (FDA Form 1572) prior to initiating this study.

15.2 IRB APPROVAL

Prior to initiating the study, the investigator at each study site will obtain written IRB approval to conduct the study. Should changes to the study protocol become necessary, protocol amendments will be submitted in writing to the IRB by the investigator for IRB approval prior to implementation. In addition, IRBs will approve all advertising materials used for subject recruitment and any educational materials (e.g., HIV/AIDS Education, Appendix III) given to the subject.

15.3 INFORMED CONSENT

All potential candidates for the study will be given a current copy of the Informed Consent Form to read. The investigator, sub-investigators, or study physician at each site will explain all aspects of the study in lay language and answer all of the candidate's questions regarding the study. If the candidate desires to participate in the study, s/he will be asked to sign the Informed Consent. No study procedure will be performed prior to signing Informed Consent. Subjects who refuse to participate or who withdraw from the study will be treated without prejudice. Two additional consent forms will be used: one for consent to allow therapy sessions to be audiotaped and one for those subjects who request HIV testing to provide informed consent for this test.

15.4 DRUG ACCOUNTABILITY

Upon receipt, the investigator/pharmacist is responsible for taking inventory of the investigational agents(s). A record of this inventory must be kept and usage must be documented. Any unused or expired investigational agent(s) shall be returned to the sponsor (or responsible party) unless otherwise instructed.
15.5 OUTSIDE MONITORING

Data and Safety Monitoring Board: Safety data will be reviewed by a data and safety monitoring board, which will meet after the first 150 subjects have completed/terminated from the study or earlier if deemed necessary. Additional meetings after that will be held on an as needed basis as determined by the medical monitor. The board will be blind to subjects' actual treatment assignments.

Medical Monitor: [name] will act as an independent medical monitor for the study. The medical monitor will be responsible for reviewing all AEs to determine whether the AE is serious and should be reported to the FDA as well as to confirm concurrence with the investigator on the severity of the AE and the relatedness to the study treatments. The medical monitor will also be responsible for tracking and assessing trends in the AEs reported.

Clinical Monitors: All investigators will allow representatives of the sponsor to periodically audit, at mutually convenient times during and after the study, all CRFs and corresponding source documents for each subject. These monitoring visits provide the sponsor with the opportunity to evaluate the progress of the study and to inform the sponsor of potential problems at the study sites. The monitors will assure that submitted data are accurate and in agreement with source documentation; verify that investigational medications are properly stored and accounted for, verify that subjects' consent for study participation has been properly obtained and documented, confirm that research subjects entered into the study meet inclusion and exclusion criteria, and assure that all essential documentation required by good clinical practices guidelines are appropriately filed.

Monitors will conduct a site initiation visit prior to the start of the study. At this visit, they will assure that proper study-related documentation exists, assist in training investigators and other site personnel in study procedures and good clinical practices guidelines, confirm receipt of study supplies, and assure that acceptable facilities are available to conduct the study.

Routine monitoring visits by the sponsor's representatives will be scheduled at appropriate intervals. At these visits, the monitors will verify that study procedures are being conducted according to the protocol guidelines. At the end of the study they will advise on storage of study records and return of unused study medication. All sites should anticipate visits by NIDA, the sponsor, and the FDA.

15.6 RECORDS RETENTION

Clinical records for all subjects studied, including history and physical findings, laboratory data, and results of consultations, are to be maintained by the investigator in a secure storage facility. These records are to be retained until notified in writing by the sponsor.

15.7 ADVERSE EVENTS REPORTING.

In accordance with FDA reporting requirements, all AEs occurring after randomization, and up to 4 weeks after completion of treatment, will be collected, documented, and reported by the investigator or sub-investigators according to the specific instructions detailed in this section of the protocol and Appendix V. The occurrence of AEs will be assessed weekly and an AE CRF completed.

An AE is defined as any reaction, side effect, or untoward event that occurs during the course of the clinical trial, whether or not the event is considered medication-related or clinically significant. For this study, AEs will include events reported by the subject, as well as clinically significant abnormal findings on physical examination or laboratory evaluation. A new illness, symptom, sign or clinically significant clinical laboratory abnormality or worsening of a pre-existing condition or abnormality is considered an AE. Stable chronic conditions, such as arthritis, which are present prior to clinical trial entry and do not worsen, are not considered AEs. All AEs must be recorded on the AE Form. The AE Form is also used to record follow-up information for unresolved events reported on previous visits.

Each week, a study investigator must review the AE Form completed for the previous week for any events that were reported as continuing. All AEs, including clinically significant abnormal findings on laboratory evaluations, regardless of severity, will be followed by study investigators until satisfactory resolution. AEs will be reported up to 4 weeks following completion of, or termination from, the study.

15.8 SERIOUS ADVERSE EVENTS

Each AE will be classified by a study investigator as serious or non-serious and appropriate reporting procedures followed. Serious adverse events (SAEs) are defined as any fatal event, any immediately life-threatening event, any permanent or substantially disabling event, any event that requires or prolongs inpatient hospitalization, or any congenital anomaly. This category also includes any event that a study investigator or the medical monitor judges to be serious or which would suggest a significant hazard, contraindication, side effect, or precaution. An unexpected event is one that is not described with respect to nature, severity, or frequency in the current Investigator's Brochure.

Any SAE (including death) due to any cause, which occurs during the course of this investigation, whether or not related to the investigational medication, must be reported within 24-hours by telephone to: the NIDA, Clinical Trials Manager, or the Study Medical Monitor, [name], or [name], NIDA Principal Investigator. The telephone report is to be followed by submission of a completed SAE Form with demographic information and a narrative explanation of the event. Attached to the SAE Form should be photocopies of the AE/ Concomitant Medications, Physical Exam, and the Medical History Forms from the subject's CRFs. Unexpected serious medical events are also to be reported immediately to the responsible institutional review board according to local regulatory requirements. All participating investigators will be notified of any serious and unexpected AE requiring submission to the FDA in an IND safety report from the sponsor.

NIDA will inform Somerset Pharmaceuticals, Inc. of all SAEs which occur during the study. Somerset, as IND holder, is required by FDA regulations to report these to the FDA in a timely fashion. All AEs that are both serious and unexpected must be reported to the FDA, in writing, within ten working days of notification of the sponsor of the SAE. If the SAE is fatal or life threatening, there is an additional obligation of Somerset to notify FDA by telephone within 3 working days, with a follow-up written report in 10 working days. There can be serious consequences including ultimately, criminal and/or civil penalties for sponsors who fail to comply with FDA regulations governing the reporting of SAEs to FDA. The site investigators in this study have the responsibility of promptly reporting all SAEs to NIDA so that Somerset can comply with these regulations.

In the event that a study subject either withdraws from the study or an investigator decides to discontinue the subject from the study due to a SAE, the subject must have appropriate follow-up medical monitoring. If the subject is hospitalized, medical monitoring will consist of not less than daily evaluation by physical examination, vital signs, laboratory evaluations, and if applicable, ECG monitoring for significant treatment-emergent abnormalities. Monitoring will continue until the problem prompting hospitalization has resolved or stabilized with no further change expected, is discovered to be clearly unrelated to study medication, or progresses to death.

16 ANALYTICAL PLAN

16.1 STATISTICAL HYPOTHESES

The primary objective of this randomized controlled trial is the assessment of the efficacy of STS in reducing cocaine use in subjects with cocaine dependence (DSM-IV criteria). It is hypothesized that STS will reduce the weekly mean proportion of days of cocaine use relative to placebo as determined by SUR confirmed with urine assays for BE.

Secondary objectives include determining the proportion of subjects that achieve measured reductions in cocaine and other drugs use (non-use days on treatment compared to non-use days at baseline), the reduction in the severity of cocaine dependence and craving (ASI, BSCS, CGI-self, and CGI-observer), severity of depression (HAM-D), and the safety of STS (AEs, laboratory data, physical exams, and vital signs) in the study population.

There is no generally accepted definition of clinically significant improvement in the treatment of cocaine dependency. The primary and secondary outcome variables are intended to explore various aspects of response to therapy and to help define a clinically meaningful response. A primary response has been chosen for its ability to indicate activity of the test product. Some of the secondary outcome variables add a measure of clinical relevance to the reduction of use by requiring either sustained abstinence or a predetermined, substantial overall reduction in use days. Other secondary outcome variables explore the need for laboratory confirmation of the SUR. Still others explore the effect of therapy on psychosocial aspects of cocaine dependency.

The primary outcome measure was selected based on a recommendation resulting from a meeting of the College on Problems of Drug Dependence (CPDD) on April 28 - 29, 1999. The consensus from this meeting was as follows:

"The consensus of the group was that the best overall outcome measure was a composite index of abstinence derived from a combination of confidential patients self-report and objective biological testing (typically urinalysis testing). The recommendation was that this composite index of abstinence be used to classify each day as abstinent or non-abstinent and that the primary outcome analysis be based on these classifications." Some data will be collected in this study for scientific use and not as primary or secondary outcome measures. Analyses of data from the RAB are included in this category. These data are being collected in order to build a database of risk behaviors associated with cocaine use.

16.2 OUTCOME MEASURES

16.2.1 Primary Outcome Measure

The basic outcome variable is the weekly proportion of cocaine non-use days. Cocaine use and non-use days will be defined by subject self-report of use, confirmed or disproved by quantification of urine BE. For the primary efficacy response, each day of the 8-week study will be coded as either a use or a non-use day based on the self-reports and on the urine BE data. Three urine collection days are scheduled per calendar week. The first day that the subject receives the investigational agent will not be scored as a use or non-use day.

Because of the pharmacokinetics of cocaine and BE, carryover from previous cocaine use may be difficult to distinguish in the laboratory from new use. The rules enunciated by Preston *et al.*¹⁷, modified to meet the conditions of this study, (Rules 1-5 below) will facilitate classification of each assessment day as use or no-use.

The following will indicate "new use":

RULE 0: Subject reports new use.

The subject self report claims no new use or SUR is missing but any of the following applies:

RULE 1:	An increase in cocaine metabolite concentration over concentration of preceding urine specimen to any value over 300 ng/ml.
RULE 2:	Both of the following occur: 1) cocaine metabolite concentration is greater than 300 ng/mL and 2) cocaine metabolite concentration is greater than one-half of the concentration measured in the preceding urine specimen.
RULE 3:	Cocaine metabolite is greater than 300 ng/ml in the first urine specimen collected in the study.
RULE 4:	If the previous urine specimen was collected more than 2 calendar days before, urine specimen with cocaine metabolite greater than 300 ng/ml.
RULE 5:	Creatinine less than 20 mg/dl and cocaine metabolite/creatinine ratio is increased compared to that of previous specimen. (Cocaine metabolite does not have to be above 300 ng/ml).

Assessment days may be less or more than 48 hours apart in this study. For this reason, the Preston rules were modified to delete reference to previous urine specimen collected at least 48 hours earlier.

Self-report gives preliminary determination of each day as a use or non-use day. Non-use days are confirmed or disproved by the urine BE data as follows:

- 1. Subject reports no new use since last urine BE or within the preceding 72 hours (whichever is the shorter time frame) but urine BE shows new use, then score the preceding day as a use day.
- 2. Self report days of non-use will be considered as missing if not followed by a urine BE assessment within 7 days. In the case of obtaining urine within 7 days, data will also be considered as missing if the concordance rate between self report and urine BE for the individual is < 70 %.
- 3. Self reports of use are accepted in all cases.

Percentage non-concordance between self-report of use and urine BE data will be calculated for each study subject as the percentage of the number of days that were scored as use days based on urine BE data overruling self-report (according to criteria in #1 immediately above) divided by the total number of urine samples analyzed, as follows:

% non-concordant = # non-concordant use days/total urine samples analyzed * 100%, thus

% concordant = 100 - % non-concordant.

The concordance rate of < 70% was established based on a survey of data sets from recently completed NIDA studies that showed that mean concordance rates ranged from 70-90%.

Appendix VI provides examples for scoring use days and non-use days according to the above rules with several combinations of SUR and urine BE data.

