1. ASI

14.3 ASSESSMENTS AT DOUBLE-BLIND STUDY TERMINATION

At the final scheduled study visit during the treatment phase of the study or if the subject discontinues prematurely, regardless of the reason (request that the subject return for final assessments), the following assessments will be performed:

- 1. If the subject discontinues prematurely, determine the reason for termination.
- 2. Physical exam
- 3. Vital signs
- 4. SUR
- 5. Urine BE and creatinine
- 6. AEs
- 7. Urine drug screen
- 8. BSCS
- 9. CGI-S
- 10. CGI-O
- 11. Hematology
- 12. Blood chemistries
- 13. Routine urinalysis
- 14. Pregnancy test (if female)
- 15. ASI
- 16. RAB
- 17. HAM-D
- 18. ECG
- 19. Treatment compliance
- 20. Concomitant medications

NOTE: Subjects that start the study on a Monday will finish the last day of the last week on a Sunday. The final assessments in these subjects will be on the next possible day after Sunday, preferably Monday. Any urine BE data collected after treatment day 56 will be used to score a day as a use or non-use day up to study day 54.

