16.4 ANALYSIS PLAN

Each of the primary and secondary efficacy outcome measures will be analyzed for the intent-totreat and for the evaluable population. Major differences in the results, if any, will be further explored. While there is every intent to be complete in describing the analyses to be performed, it is not possible to anticipate every contingency and some adjustments may be required to meet constraints posed by the structure of the data.

All statistical tests will be two-sided at a 5% level of alpha. Confidence intervals will be two-sided with a 95% confidence coefficient.

Primary Efficacy Outcome

The primary outcome variable for each subject is the weekly proportion of cocaine non-use days. Each subject's weekly proportion is equal to the number of his/her cocaine non-use days divided by the number of his/her non-missing study days during that week (a maximum of 6 days for week 1 and 7 days for weeks 2 through 8).

The weekly mean proportion of cocaine non-use days on study will be compared between treatment groups using Generalized Estimating Equations (GEE). GEE provide a model-based regression methodology applicable for the analysis of the correlated data that will result from this repeated measures longitudinal study.

The GEE procedure proposed by Liang and Zeger¹⁸ and Zeger and Liang¹⁹ (Biometrics, 1986) model the population average and has several useful features:

- 1. It can be used to analyze different types of outcomes such as continuous, binary, or count.
- 2. It can be used to analyze an unbalanced design caused by either differing numbers of observations per person or by observations taken at different times.
- *3.* The parameter estimates are consistent even if assumptions about the variance structure are not completely accurate.

Secondary Efficacy Outcomes

As a secondary analysis, the baseline proportion of cocaine non-use days, site, gender, diagnosis of ADD, severity of depression during screening, and their first-order interactions with treatment will also be included in the model. Presentation will include the full model with all terms and a reduced model containing only significant terms.

Unless the primary response analysis implies the need for a more elaborate model, between group comparisons of the secondary outcomes will be performed as follows:

- 1. Proportion of successful subjects, measures A, B, and C, will be assessed by Chi-square tests.

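### Below 70% concordance the primary scoring can delete urine-confirmed non-use days but never self-reported use days, so missing data depend on the outcome

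*Protocol*

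**What the plan says.** Protocol 16.2.1 codes each treatment day from self-report and then checks denials against urine benzoylecgonine (BE). Three numbered rules matter.

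- Item 1: when a urine contradicts a denial, "then score the preceding day as a use day".
- Item 2: "Self report days of non-use will be considered as missing if not followed by a urine BE assessment within 7 days". Even with a urine inside that window, "data will also be considered as missing if the concordance rate between self report and urine BE for the individual is < 70"%.
- Item 3: "Self reports of use are accepted in all cases".

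Concordance is 100% minus the non-concordance percentage, defined as "non-concordant = # non-concordant use days/total urine samples analyzed * 100"%. The only reason given for the 70% limit is a survey of earlier studies in which "mean concordance rates ranged from 70-90"%.

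Section 16.4 defines the primary variable as non-use days divided by non-missing days in each week, with "a maximum of 6 days for week 1 and 7 days for weeks 2 through 8". The note in 14.3, on subjects who start on a Monday, says urine collected after day 56 "will be used to score a day as a use or non-use day up to study day 54".

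**The concern.** Item 2 removes denials and item 3 protects admissions. Non-use days of a flagged subject leave both numerator and denominator, including days closed by a urine that shows no new use. Reported use days stay. Every weekly value left for that subject is then 0% or absent, so the recorded non-use can only fall or vanish.

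Only a urine showing new use can make a subject non-concordant. Days are therefore deleted because of cocaine use after randomisation, which is the outcome itself, and treatment may change how often it happens. GEE's tolerance of unequal numbers of observations, cited in 16.4, does not cover missingness driven in this way. At stake are the meaning of the primary endpoint, the loss of laboratory-confirmed abstinence (for example in someone who under-reports early and then stops), and added all-or-nothing variation.

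**Working it through.** **Inputs.** Urines: 3 × 8 = 24 (16.2.1). Scorable days: 6 + 7 × 7 = 55 (16.4). Cut-off 70%. Planned effect 10 points, SD 33.5, power 80%, two-sided 5%, 110 per arm (16.4, 16.6).

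**The plan's own figure.** For one measurement, n = 2(1.96 + 0.84)² × 33.5² / 10² ≈ 176 per arm (177 rounded up). For eight equally correlated weekly values, multiply by (1 + 7ρ)/8. The protocol gives no ρ; 110 is reached at ρ ≈ 0.57 (ρ = 0.5 gives 99, ρ = 0.6 gives 115). The figure is plausible but cannot be confirmed, and 16.6 states no allowance for the concordance rule.

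**The step at 70%.** Take a subject whose use days are all urine-overruled denials.

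| Discordant urines of 24 | Concordance | Non-use without deletion | Under item 2 |
|---|---|---|---|
| 7 | 1 − 7/24 = 70.8% | 48/55 = 87.3% | 87.3% |
| 8 | 1 − 8/24 = 66.7% | 47/55 = 85.5% | 0% in each week with an overruled day if those days are kept; no data if they also go missing |

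With a 25th (termination) urine the step falls at the same count: 72.0% against 68.0%. A dropout with 3 urines fails on a single discordant one (66.7%).

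**Example.** Overruled at 8 urines in weeks 1 to 3 and clean in weeks 4 to 8, a subject loses all 5 × 7 = 35 later days. If overruled days are kept, what remains is 0% for weeks 1 to 3 and nothing after.

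**How many subjects.** The cut-off equals the lowest study mean cited. The between-subject spread is not given, so it is assumed: the number of discordant urines out of 24 is binomial, or beta-binomial with parameters summing to 20, 10, 5 or 2. The share with 8 or more is:

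- mean concordance 90%: 0.2 to 12%
- 80%: 9 to 26%
- 70%: 40 to 44%

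**Power.** None of the inputs below is in the protocol. One simulation had 110 per arm and 2,000 resampled trials. Daily use varied between subjects and weeks, each subject had their own probability of reporting use, and urines were taken Monday, Wednesday and Friday. Treatment also lowered the share flagged.

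| Mean concordance | No deletion | Deletion, all use days kept | Deletion, only self-reported use kept |
|---|---|---|---|
| about 93% | 83% | 80% | 80% |
| about 89% | 78% | 70% | 72% |
| about 78% | 83% | 59% | 62% |

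In the last row the difference between arms grows (7.6 to 11.1 points), but the weekly SD rises from 0.250 to 0.388; the loss comes through variance. A separate simulation gave 73% falling to 45% at mean concordance 72%. With flagged subjects wholly missing it gave 73% to 68%, 77% to 75% and 77% to 76% at mean concordance 72%, 84% and 92%.

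A cruder calculation scores a share f of both arms 0 regardless of their use, with placebo means of 40 to 60%. At f = 10% power falls from 80% to 55–65%. It ignores the link between use and flagging, so I use it only to show how far the answer moves with the assumptions.

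**Day 54.** For a Monday starter, day 54 is the Friday of week 8, day 56 the Sunday and day 57 the Monday of the final urine. Item 1 would let that urine overrule day 56, and 16.4 allows seven days in week 8. The 14.3 note stops its use at day 54.

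**The case against.** Distrusting denials from someone repeatedly contradicted by urine is a deliberate, stated choice, applied identically in both arms. A reader might infer type I error inflation; none has been shown. Secondary outcomes C and D (self-report only) and F (urine BE level) do not use the rule. The three-urine dropout is outside the evaluable population, which needs four urines, though inside intent-to-treat. These points stand, and they lower the severity.

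A reader might also infer that every use day is kept, so that 87% always turns into 0%. The text does not say so. Item 3 protects self-reported use only, item 2 does not define data, and the scoring examples in Appendix VI were not available here. If overruled days also go missing, the subject in the table has no primary data at all. That does not rescue the rule: a randomised subject then contributes nothing, and any flagged subject who admits use still scores 0% in that week. Treating flagged subjects as wholly missing, which costs least power, conflicts with item 3 for anyone who reports use. Nor is 87% a true value, since item 1 scores one day per contradicted urine and real use may be higher.

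It is tempting to state as fact that much of the power is lost. The documents do not support that. The loss depends on the spread of concordance, the placebo mean and the effect of treatment on flagging. If the 33.5% SD from the oral selegiline study (CS-1017) came from data scored the same way, part of the extra variance is already counted; the protocol does not say.

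On day 54, one might conclude that non-use on days 55 and 56 is missing while use counts. The note can equally be read as ending the scoring window for both, seven days is only a maximum, and a day-57 urine does fall within 7 days.

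**Conclusion.** The point holds as a one-sided scoring rule in the primary endpoint. Below 70% concordance, confirmed non-use can be deleted while self-reported use cannot, the deletion depends on post-randomisation use, and recorded non-use is pushed downward. The step between 7 and 8 discordant urines of 24 is exact arithmetic; whether the eighth leads to 0% weeks or to no data depends on an undefined word. Because the cut-off equals the lowest mean the protocol cites, a non-trivial share of subjects may be affected.

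The power cost is a range under assumed inputs. It is about 3 points at mean concordance near 93% and about 25 to 30 points at 72 to 78% when use days are kept, or about 1 to 5 points if flagged subjects are wholly missing. Some of it may already sit in the planning SD.

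The day-54 wording is a minor inconsistency, confined to week 8 of Monday starters. Overall this should be fixed; the material does not show that the trial fails without the change.

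**What to change.** Before unblinding:

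1. Remove the subject-level 70% deletion from the primary scoring in 16.2.1.
2. Keep as non-use any reported non-use day closed within 7 days by a urine showing no new use, whatever the subject's overall concordance. Leave the item 1 overruling rule as it is.
3. Where data are still set to missing, treat use and non-use days alike.
4. Run the 70% deletion as a sensitivity analysis, stating which days become missing: denials only, overruled days too, or all of the subject's days.
5. Reconcile the day-54 limit in 14.3 with the preceding-day rule in 16.2.1 and the seven-day week 8 in 16.4, for example by changing it to day 56.

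The cost is a change of text and scoring program, with no new data. The downsides are less comparability with studies scored by the 70% rule, which the sensitivity analysis partly restores, and more weight on the denials of poor reporters.
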